Prospective enrollment from November 2020 to October 2021 in 60 Italian surgical centers. All patients undergoing elective or delayed urgency colorectal surgery with anastomosis will be included in a prospective database after written informed consent. A total of 3,000 patients is expected based on a mean of 50 cases per center.

Inclusion criteria

1. Patients submitted to laparoscopic/robotic/open/converted ileo-colo-rectal resection with anastomosis, including planned Hartmann's reversals.
2. American Society of Anesthesiologists' (ASA) class I, II or III
3. Elective or delayed urgency surgery
4. Patients' written acceptance to be included in the study.

Exclusion criteria

1. American Society of Anesthesiologists' (ASA) class IV-V
2. Emergent surgery
3. Pregnancy
4. Hyperthermic intraperitoneal chemotherapy for carcinomatosis.

Outcome measures

1. Preoperative risk factors for morbidity (age, gender, obesity, nutritional status, diabetes, cardiovascular disease, chronic liver disease, renal failure, inflammatory

bowel disease, perioperative steroid therapy, ASA class I-II vs III, SARS-CoV-2 infection)

2. Operative parameters (approach, procedure, anastomotic technique, length of operation, pTNM stage)
3. Adherence to ERAS program (28, 29) items (Tab.1).

Endpoints

Primary

1. Patient-related outcomes measures (PROMs):
 - a. Euro-QoL Group EQ-5D-5L (EQ-5D-5L, 32);
 - b. MD Anderson Symptom Inventory for gastrointestinal surgery patients (MDASI-GI, 33);
 - c. Functional Assessment of Cancer Therapy – Colorectal (FACT-C, 34)
2. Return to intended oncologic therapy (RIOT, 24)

Secondary

3. Anastomotic leakage rate
4. Minor and major complication rates according to Clavien-Dindo (35, 36) and JCOG (37) classification
5. Overall length of postoperative hospital stay (including any readmission)
6. Difference between date of readiness for discharge (RFD, 38) and date of actual discharge
7. Readmission and reoperation rates
8. Comparison of two nutritional status scores, MNA-SF (30) and PNI (31), regarding anastomotic leakage, minor and major complication rates and RIOT (24)

9. Impact of anastomotic testing through air-leak test (ALT) and near-infrared fluorescence (NIR) narrow-band imaging (NBI) using indocyanine green (ICG) on anastomotic leakage rates

Recorded data and follow-up

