Potential patient-specific and intraoperative risk factors will be recorded: gender, body mass index, nutritional status, frailty (39), surgical indication (cancer, polyps, chronic inflammatory bowel disease, diverticular disease), use of steroids, renal failure and dialysis, cardiovascular or respiratory disease, American Society of Anesthesiologist class, bowel preparation, type of approach, level of anastomosis and technique (mechanical or hand-sewn, intra- or extra-corporeal), operative time, presence of drainage, and perioperative blood transfusion(s). During the postoperative period, patients will be examined by the attending surgeon daily. Fever (central temperature > 38 °C), pulse, abdominal signs, bowel movements, volume and aspect of drainage (if present) will be recorded daily. The local attending surgeon will make any decision for complementary exams and imaging according to his own criteria, the only exception being the creation of a proximal diverting stoma at operation, that mandates routine check of anastomotic integrity through an intraluminal contrast exam (standard x-rays or CT scan), MRI, or direct endoscopic evaluation three to six weeks after the operation. The rate of any adverse event will be calculated and graded according to Clavien-Dindo criteria (35, 36) and to Japan Clinical Oncology Group Postoperative Complications (JCOG-PC) extended criteria (37), including all anastomotic leaks, wound infection (according to the definitions of the Centers for Disease Control and Prevention and wound culture, 40), pneumonia (clinical symptoms, and physical and radiological examinations), central line infection (positive blood culture), urinary tract infection (positive urine

culture with bacterial count). Patients will be followed-up in the outpatient clinic up to 8 weeks after discharge from the hospital.

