Anastomotic dehiscence (any deviation from the planned postoperative course related to the anastomosis, or presence of pus or enteric contents within the drains, presence of abdominal or pelvic collection in the area of the anastomosis on postoperative CT scan, leakage of contrast through the anastomosis during enema or evident anastomotic dehiscence at reoperation for postoperative peritonitis) will be defined and graded according to international consensus guidelines (41). Anastomotic testing will be performed intraoperatively with the air-leak test (ALT) and using ICG-NIR-NBI with a standard protocol [*ICG 25 mg diluted in 10 mL water (2.5 mg/mL); first bolus i.v. injection of 4 mL (10 mg) after vascular control and mesenteric division, just before proximal and/or distal bowel division; second bolus i.v. injection of 4 mL (10 mg) just before joining anastomotic stumps; third (optional) bolus i.v. injection of 2 mL (5 mg) after the anastomosis is completed; NIR-NBI observation within 120-180" after every ICG injection (direct, laparoscopic or endoscopic)*].

PROM questionnaires (32-34) will be administered to all enrolled patients four to one week before the planned operation, on the day of discharge, and 6 weeks after the operation.

RIOT (24) rates will be recorded in all patients submitted to surgery for malignancy, according to national guidelines for colorectal cancer (42).

After anonymization, all data of each single case will be prospectively uploaded by local investigator(s) on a protected web-based database and incorporated into a spreadsheet for data analysis, checking for any discrepancy, that will be addressed and solved through strict cooperation between chief investigator, data manager and participating centers.

Ethics and dissemination

The study will be conducted according to the Helsinki declaration and to the Guideline for good clinical practice E6(R2) principles. This study protocol will be submitted to the coordinating
ALL 3 – Protocollo dello Studio

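### Only patients with a diverting stoma have a mandatory check of the anastomosis, and a contrast leak counts without symptoms, so the leakage rate depends partly on who had a stoma

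*Protocol*

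**What the plan says.** Under 'Recorded data and follow-up', the protocol sets the default for postoperative imaging: "The local attending surgeon will make any decision for complementary exams and imaging according to his own criteria". It allows one departure, "the only exception being the creation of a proximal diverting stoma at operation, that mandates routine check of anastomotic integrity". That check may be an intraluminal contrast study (x-ray or CT), "MRI, or direct endoscopic evaluation three to six weeks after the operation". Outpatient follow-up runs to 8 weeks after discharge, so the check falls inside it.

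The same section defines anastomotic dehiscence by a list of alternatives. Besides clinical signs, it includes "presence of abdominal or pelvic collection in the area of the anastomosis on postoperative CT scan" and "leakage of contrast through the anastomosis during enema or evident anastomotic dehiscence at reoperation for postoperative peritonitis". The contrast criterion requires neither symptoms nor a change in management. Leaks are graded by a cited consensus, but the protocol does not restrict the rate to particular grades.

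Under 'Endpoints', "Anastomotic leakage rate" is secondary endpoint 3. Leakage is also an outcome in endpoint 8 (MNA-SF against PNI) and endpoint 9 (air-leak test and ICG fluorescence). Under 'Statistical Analysis', variables enter the multivariable model if they are significant on univariate analysis. A diverting stoma is named neither among the recorded risk factors nor among the operative parameters.

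**The concern.** Two rules that are each reasonable combine badly. One fixes who is examined without clinical suspicion: stoma patients only. The other fixes what counts as a leak: a contrast finding is enough. A silent leak in a stoma patient is likely to be found and counted. The same leak in a patient without a stoma is found only if the local surgeon happens to order a study.

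This is differential ascertainment of an outcome. It raises the observed leakage rate in proportion to stoma use. It also distorts any comparison in which stoma use differs between groups, making the group with more stomas look worse at equal true risk. Endpoint 9 is the most exposed, because it compares leakage by intraoperative testing, and a test result may plausibly influence the decision to divert (an assumption; the protocol does not say so). In endpoint 8 each score's AUC and Youden cut-off could shift if the score is associated with stoma creation.

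An analysis plan can choose how to handle the two kinds of leak only if the data show how each leak was found. The protocol does not ask for this.

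**Working it through.** The protocol states no leak rate, stoma rate or leak-based sample size, so there is no figure of its own to reproduce. The calculation below is an illustration, and every input is an assumption.

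**Inputs.** c = clinically evident leak rate, the same with and without a stoma. q = silent leak rate, also the same in both. d = share of silent leaks found by discretionary imaging in patients without a stoma. s1, s2 = stoma use in the two groups compared.

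**Formulas.**
- Observed rate with a stoma: c + q.
- Observed rate without a stoma: c + d·q.
- Observed rate in group i: r_i = s_i(c + q) + (1 − s_i)(c + d·q).
- Spurious odds ratio: [r2/(1 − r2)] / [r1/(1 − r1)].

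True risk is identical throughout, so the correct odds ratio is 1.

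**Scenario set A:** c = 4-6%, q = 2-4%, d = 0-25%, stoma use 10% against 20% or 5% against 30%.
- Smallest bias (c = 6%, q = 2%, d = 25%, 10% against 20%): the rate is 8% with a stoma and 6.5% without. Group rates are 6.65% and 6.80%, a difference of 0.15 percentage points and an odds ratio of 1.02.
- Largest bias (c = 4%, q = 4%, d = 0, 5% against 30%): 8% with and 4% without. Group rates are 4.2% and 5.2%, a difference of 1.0 point and an odds ratio of 1.25.

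**Scenario set B:** c = 4-6%, q = 2-8%, d = 0, stoma use 10% against 30%.
- Smallest (c = 6%, q = 2%): group rates 6.2% and 6.6%, odds ratio 1.07.
- Largest (c = 4%, q = 8%): group rates 4.8% and 6.4%, odds ratio 1.36.

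Together the two sets span about 1.02 to 1.36. They are not fully crossed. Pairing the highest silent rate of set B with the widest stoma contrast of set A (c = 4%, q = 8%, d = 0, 5% against 30%) gives 4.4% and 6.4%, an odds ratio of 1.49.

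**Boundary check.** With d = 1 the two observed rates are equal and the bias is zero. The effect comes from unequal detection alone.

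**The case against.** Several points on the other side have force.

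- **Much of this could sit in an analysis plan.** Which grades enter the main leak analysis, and any sensitivity analysis, are commonly settled there, and every leak is already graded. That stands for the choice of analysis. It does not answer the data gap: grade does not show whether a leak was first found at the mandated check.
- **Stoma status is partly recoverable.** The FACT-C form asks about an abdominal stoma and is given at discharge and at 6 weeks. Level of anastomosis is recorded as well. Both help, but one is a questionnaire reply and the other a proxy, and neither shows how a leak was found. The appendix material between FACT-C and the Edmonton Frail Scale was not available to us, so a relevant field there cannot be excluded.
- **Endpoint 8 is only partly exposed.** Both scores are compared in the same patients on the same outcome, so their difference is distorted only if they differ in their association with stoma. This stands.
- **Counting only clinically suspected leaks could reverse the bias.** Diversion may mask symptoms, so such an outcome could undercount leaks in stoma patients, and it would still depend on local criteria at 60 centres. This is reasoning and not a statement in the protocol, but it is a good argument against replacing the main outcome.
- **The contrast criterion does not cover every check.** MRI or endoscopy may be used, while the definition names a CT collection and an enema leak. Its clause on any deviation from the planned course is broad, so this narrows the asymmetry at most.

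A reader might infer two stronger claims. The first is a spurious odds ratio of 1.4-3.3, which the same assumptions give for stoma against no stoma when d = 0 (8% against 6%, up to 12% against 4%). That contrast is not an endpoint. The second is that low ERAS adherence would falsely appear to cause leaks. The protocol does not support a link between adherence and stoma use: its adherence table excepts bowel preparation when a covering stoma is anticipated, and makes allowances for pelvic surgery.

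**Conclusion.** The concern holds in a limited form. Followed as written, the protocol searches for silent leaks systematically only in stoma patients, counts them in one undivided outcome, and adjusts for stoma only if it happens to be recorded and significant on univariate analysis. Endpoints 3 and 9, and to a lesser degree the individual AUCs and cut-offs in endpoint 8, may be biased where stoma use differs.

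The size is modest: odds ratios of about 1.02-1.36 at equal true risk in the scenarios shown. It depends on assumed silent-leak rates, stoma use and discretionary detection, and on a clinical leak rate that is equal with and without a stoma. None of these comes from the protocol. The primary endpoints (PROMs and RIOT) and both sample sizes do not rest on leakage. This is a worthwhile, inexpensive improvement and not a flaw that undermines the study.

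**What to change.** Leave the leak definition and the imaging rules as they are, and add the following:

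1. Record whether a diverting stoma was created at operation.
2. For each leak, record one flag: first found at the mandated routine check, yes or no.
3. Report leaks found on clinical suspicion and leaks found only at the routine check separately.
4. Repeat the leak analyses of endpoints 3, 8 and 9 as a sensitivity analysis that excludes leaks found only at the routine check and is stratified by, or adjusted for, stoma regardless of univariate significance.

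The cost is one or two database fields and some extra analysis, with no added imaging. The flag is easiest to capture prospectively. Because the clinically suspected analysis may undercount leaks masked by diversion, it should accompany the main outcome and not replace it.

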center ethics committee (Comitato Etico Regionale delle Marche - C.E.R.M.) for approval and then registered at ClinicalTrials.gov (NCT04397627). Thereafter, all the participating centers will obtain authorization to participate from the local institutional review board. The results of the study are intended to be presented at national and international medical congresses on corresponding fields of interest (colorectal surgery, abdominal surgery). Written publications of the results are planned within surgical journals. The authorship for written publications is confirmed to all participating investigators, only being granted in the case of substantive contributions to the design, conduct, data analysis, collection and interpretation. Anonymized participant-level datasets will be available after study completion upon reasonable request by contacting the principal investigator.

Statistical Analysis

Quantitative values will be expressed as mean \pm standard deviation (SD), median and range; categorical data with percentage frequencies. For categorical data, analysis will include the use of cross tabulation, chi squared or Fisher's exact test where indicated. Continuous or discrete variables will be analyzed using Student's two-sided t test (allowing for heterogeneity of variances) or with a non-parametric test (Mann-Whitney U test or Kruskal-Wallis test as indicated). Joint and conditional multivariate association between all variables shown to be significant on univariate analysis will be assessed using binary logistic or multiple linear regression. The odds ratio (OR) will be presented followed by 95% confidence interval (95% CI). Concerning comparison of nutritional status scores, areas under the receiver-operating characteristics curve (AUC-ROC) will be calculated for all endpoints, considering values from 0.7 to 0.8 as acceptable, 0.8 to 0.9 excellent, and above 0.9 as outstanding (43). Differences in AUC-ROC curves will be analyzed with the chi-squared test. Optimal cut-off points will be obtained applying Youden's Index (Sensitivity+Specificity-1), choosing those values of the AUC-ROC curve where this index is

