maximal. Negative predictive values (NPV) and positive predictive values (PPV) will also be calculated; finally, a logistic regression model will be built using the presence/absence of endpoint as dependent variable, and nutritional scores \leq or $>$ the cut-off values as explanatory factors; using logistic transformation of the linear predictors, the probabilities of the endpoint related to the different combinations of factors level will be obtained (44). For all statistical tests the significant level is fixed at $p < .05$. Statistical analyses will be carried out using STATA software (Stata Corp. College Station, Texas, USA).

Sample size

Adherence to at least 70% of the ERAS program items was identified as a cut-off for significant improvement of outcomes (18), with a 2:1 expected ratio below:above the cut-off. Estimating a reduction of postoperative PRO from preoperative baseline (1.0) at 0.7 for adherence above the cut-off and at 0.64 for adherence below the cut-off (44), alpha 0.04, beta 0.8, the required sample size is $n=2,406$ (802 cases above 70% adherence and 1,604 below 70% adherence). Reported rates for failure to RIOT and ERAS program items adherence below or above 70% are 13 and 6.5%, respectively (27); the required sample size for evaluation of failure to RIOT is $n=885$ (295 cases above 70% adherence and 590 below 70% adherence). Based on previous iCral observational study on colorectal surgery in Italy (44, 46, 47), the expected ratio of malignant:benign indications to surgery is 70:30 (2,100 resections for malignancy and 900 resections for benign disease on the basis of 3,000 expected cases).

References

2. Kehlet H (2008) Fast-track colorectal surgery. *Lancet* 371:791–793.

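### Secondary endpoint 9 asks for the impact of air-leak and ICG testing, but the protocol leaves open whether testing is mandatory, and its univariate screen can drop the testing term because of confounding by level of anastomosis

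*Protocol*

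**What the plan says.** Endpoints, Secondary, item 9 reads: "Impact of anastomotic testing through air-leak test (ALT) and near-infrared fluorescence (NIR) narrow-band imaging (NBI) using indocyanine green (ICG) on anastomotic leakage rates". It names no comparison group.

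Recorded data and follow-up gives the instruction on use: "Anastomotic testing will be performed intraoperatively with the air-leak test (ALT) and using ICG-NIR-NBI with a standard protocol". A bracketed account of ICG dilution, bolus timing and observation window follows. The only step marked as optional is the last injection: "third (optional) bolus i.v. injection of 2 mL (5 mg) after the anastomosis is completed". The sentence names no population. The neighbouring sentences do: the PROM questionnaires "will be administered to all enrolled patients", and RIOT "rates will be recorded in all patients submitted to surgery for malignancy".

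The design is an observational database: "All patients undergoing elective or delayed urgency colorectal surgery with anastomosis will be included in a prospective database after written informed consent".

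The adjustment rule is in Statistical Analysis: the association between "all variables shown to be significant on univariate analysis will be assessed using binary logistic or multiple linear regression". The same section sets the threshold: "For all statistical tests the significant level is fixed at" p < .05. Level of anastomosis is among the recorded risk factors in Recorded data and follow-up, but no model is required to include it.

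**The concern.** An impact of testing is most naturally read as leakage in tested compared with untested patients, so the study needs untested patients. The sentence on use neither requires testing in everyone nor leaves it to the centre, and the 60 centres could act on it differently. A centre that treats it as mandatory supplies no comparators, and no later analysis document can create them.

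If use does vary, surgeons may test the riskier anastomoses more often. A protective effect would then be masked in the crude comparison. The stated rule decides on that crude comparison whether testing reaches the adjusted model at all. A real benefit could be set aside before the adjustment that would reveal it.

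**Working it through.** **Text.** Two readings of the sentence on use are possible.

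- Mandatory: every patient has both tests. One of the four ALT-by-ICG combinations is filled, so tested versus untested cannot be estimated. Leakage by test result still can.
- Technique specification: the bracketed protocol says how ICG is done when it is done. This fits the observational design and gives a contrast, but a non-randomised one.

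**The screen under the second reading.** The protocol gives no figure for endpoint 9, so there is none to reproduce. From the protocol: n = 3,000 and the .05 threshold. Assumed: 30% low anastomoses; untested leakage 8% (low) and 4% (other); true odds ratio for testing 0.7 in both groups; testing more frequent in low anastomoses.

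Leakage in tested patients:
- low: odds 0.7 × 0.08/0.92 = 0.0609, risk 5.74%
- other: odds 0.7 × 0.04/0.96 = 0.0292, risk 2.83%

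Crude contrast when 60% of low and 40% of other anastomoses are tested:
- tested: share 0.3×0.6 + 0.7×0.4 = 0.46; leakage (0.18×5.74% + 0.28×2.83%)/0.46 = 3.97%
- untested: share 0.12 + 0.42 = 0.54; leakage (0.12×8% + 0.42×4%)/0.54 = 4.89%
- crude odds ratio (0.0397/0.9603)/(0.0489/0.9511) = 0.80

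Chance of passing the screen (two-sided test of proportions):
- pooled leakage 4.47%; SE = √[0.0447 × 0.9553 × (1/1,380 + 1/1,620)] = 0.00757
- z = 0.00919/0.00757 = 1.21
- P(Z > 1.96 − 1.21) ≈ 23%

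The same steps at 80%/30% give 4.38% tested, 4.44% untested and a crude odds ratio of 0.99. The screen then passes testing about as often as chance, 5%.

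Simulation (10,000 studies per row; chi-squared screen against a logistic model with testing and level both forced in):

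| Tested, low/other | Crude OR | Testing passes screen | Testing significant, level forced |
|---|---|---|---|
| 50%/50% | 0.70 | 51% | 51% |
| 60%/40% | 0.80 | 23% | 50% |
| 70%/40% | 0.86 | 13% | 48% |
| 80%/30% | 0.99 | 5% | 41% |

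The forced model recovers a median odds ratio of about 0.70 throughout. Independent re-runs agree to within about 2 percentage points.

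**Level dropped while testing stays.** This is the other way the screen could bias the estimate. Over 60%/40% to 80%/30% use it occurs in about 2% of studies or fewer at leakage 8% v 4%, about 13–20% at 6% v 4%, and almost never at 10% v 4%. At 6% v 4% the bias is also small: with 60%/40% use the crude odds ratio is 0.76 against a true 0.70.

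**The case against.** The strongest reply is that the sentence on use runs straight into dilution and timing, names no population, and sits in an observational study, so it specifies technique. Endpoint 9 itself presupposes that use varies. This largely stands. A reader might infer that the protocol contradicts itself and that endpoint 9 cannot be estimated, but the documents do not support that: the conflict arises only if testing is mandatory, and even then leakage by test result is estimable. What remains is that the protocol does not say which reading applies.

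Second, the regression sentence is generic and does not expressly forbid keeping an exposure of interest in the model. That is fair. But it is the only selection rule given, it makes no exception for endpoint 9, and an analysis plan that forced testing in would depart from it.

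Third, all inputs except the sample size and threshold are assumed, and even the forced model detects an odds ratio of 0.7 in only about 40–50% of studies. Both points are correct. The fix removes the loss caused by the screen but does not make the endpoint well powered.

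A reader might also object that no term represents the 60 centres. That is not part of this point. A centre term is something an analysis plan not shown here could add, and any harm from leaving it out rests wholly on assumed differences between centres.

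**Conclusion.** The point holds in a limited form. The protocol leaves unclear whether ALT and ICG are mandatory. If use varies, its stated screen can discard the testing term because of confounding by level of anastomosis.

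Under the inputs above, the chance that testing reaches the adjusted model falls to about 23% (60%/40% use) and 5% (80%/30%), against about 50% and 40% significant with level forced. There is no loss when use is unrelated to level. The size therefore depends on how strongly testing follows risk, which the protocol does not state.

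Level alone fails the screen in 55–76% of studies at leakage 6% v 4%, and a reader might take that as the rate of harm. It is not: the estimate is affected only when testing is kept and level dropped, the smaller problem sized above.

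The point concerns one secondary endpoint. The primary endpoints and their sample sizes are unaffected.

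**What to change.** 1. In Recorded data and follow-up, state that use of ALT and of ICG follows local practice, and that the bracketed technique applies when ICG is used.
2. Define endpoint 9 as leakage in tested versus untested patients, separately for ALT and ICG.
3. In that model, enter the testing term and level of anastomosis whatever their univariate p values.
4. Report the result as an adjusted association, not an impact.
5. If testing is truly mandatory, redefine endpoint 9 as leakage by test result.

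The cost is one clause on use, the wording of one secondary endpoint and one sentence on its model. The price is a more modest claim. Confounding by factors other than level may remain and should be acknowledged.

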Appendix 5 MD Anderson Symptom Inventory for gastrointestinal surgery patients (MDASI-GI) (33)

Data compilazione / / ; preop ; dimissione ; tardivo

I Parte: Come sono I tuoi sintomi? Le chiediamo quanto ritiene che i suoi sintomi siano stati forti nelle ultime 24 ore. Per favore selezioni per ogni elemento un numero da 0 (sintomi assenti) a 10 (sintomi presenti al massimo).

1 Dolore	0	1	2	3	4	5	6	7	8	9	10
2 Stanchezza	0	1	2	3	4	5	6	7	8	9	10
3 Nausea	0	1	2	3	4	5	6	7	8	9	10
4 Sonno disturbato	0	1	2	3	4	5	6	7	8	9	10
5 Non sentirsi a proprio agio	0	1	2	3	4	5	6	7	8	9	10
6 Affanno	0	1	2	3	4	5	6	7	8	9	10
7 Non ricordare le cose	0	1	2	3	4	5	6	7	8	9	10
8 Mancanza di appetito	0	1	2	3	4	5	6	7	8	9	10
9 Sonnolenza	0	1	2	3	4	5	6	7	8	9	10
10 Secchezza delle fauci	0	1	2	3	4	5	6	7	8	9	10
11 Tristezza	0	1	2	3	4	5	6	7	8	9	10
12 Vomito	0	1	2	3	4	5	6	7	8	9	10
13 Formicolii	0	1	2	3	4	5	6	7	8	9	10
14 Stitichezza	0	1	2	3	4	5	6	7	8	9	10
15 Diarrea (feci liquide)	0	1	2	3	4	5	6	7	8	9	10
16 Difficoltà a deglutire	0	1	2	3	4	5	6	7	8	9	10
17 Alterazione del gusto	0	1	2	3	4	5	6	7	8	9	10
18 Sensazione di gonfiore	0	1	2	3	4	5	6	7	8	9	10

II Parte: Quanto i suoi sintomi hanno interferito con la sua vita? Quanto i suoi sintomi hanno interferito con i seguenti elementi nelle ultime 24 ore? Per favore selezioni per ogni elemento un numero da 0 (i sintomi non hanno interferito) a 10 (i sintomi hanno interferito completamente).

19 Attività quotidiana	0	1	2	3	4	5	6	7	8	9	10
20 Umore	0	1	2	3	4	5	6	7	8	9	10
21 Lavoro (anche domestico)	0	1	2	3	4	5	6	7	8	9	10
22 Rapporto con altre persone	0	1	2	3	4	5	6	7	8	9	10
23 Camminare	0	1	2	3	4	5	6	7	8	9	10
24 Godimento della vita	0	1	2	3	4	5	6	7	8	9	10

**Appendix 6 Functional Assessment of Cancer Therapy – Colorectal® FACT-C (34)**Data compilazione / / ; preop ; dimissione ; tardivo *Sotto abbiamo elencato delle affermazioni ritenute importanti da persone con la sua stessa malattia. **La preghiamo di cercare o contrassegnare un solo numero per riga per indicare la sua risposta in riferimento agli ultimi 7 giorni.***

BENESSERE FISICO		Per Niente	Un po	Abbastanza	Molto	Moltissimo
GP1	Mi manca l'energia	0	1	2	3	4
GP2	Ho nausea	0	1	2	3	4
GP3	Ho difficoltà ad occuparmi delle necessità della mia famiglia a causa delle mie condizioni fisiche	0	1	2	3	4
GP4	Ho dolori	0	1	2	3	4
GP5	Mi danno fastidio gli effetti collaterali della cura	0	1	2	3	4
GP6	Mi sento male	0	1	2	3	4
GP7	Sono costretto a trascorrere del tempo a letto	0	1	2	3	4

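### The PRO endpoint is sized as a fraction of baseline but tested with unadjusted two-sample tests; nothing ensures that the preoperative score enters the comparison, and the fraction does not fit MDASI-GI

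*Protocol*

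**What the plan says.** The protocol's Endpoints section lists three primary questionnaires: EQ-5D-5L, MDASI-GI and FACT-C. Under Recorded data and follow-up, all enrolled patients complete them "four to one week before the planned operation", on the day of discharge and six weeks after surgery. The inclusion criteria admit "Elective or delayed urgency surgery"; the second category is not defined.

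The Sample size section sets the PRO effect as follows: "Estimating a reduction of postoperative PRO from preoperative baseline (1.0) at 0.7 for adherence above the cut-off and at 0.64 for adherence below the" cut-off. It names neither an instrument nor a time point. It continues with "alpha 0.04, beta 0.8, the required sample size is" 2,406, split into 802 patients above and 1,604 below 70% adherence.

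The Statistical Analysis section gives one general rule for continuous or discrete variables: a "two-sided t test (allowing for heterogeneity of variances) or with a non-parametric test". Binary logistic or multiple linear regression follows, restricted to variables found significant in univariate analysis. The section does not say whether the PRO variable tested is the postoperative score, the change or the fraction. The preoperative PRO score is not among the risk factors listed under Outcome measures or Recorded data and follow-up.

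Appendix 5 scores each MDASI-GI symptom with "un numero da 0 (sintomi assenti) a 10 (sintomi presenti al massimo"). Appendix 4 codes the EQ-5D-5L items in the opposite direction, with 5 for no problem and 1 for the worst level.

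**The concern.** Adherence to the ERAS items is observed, not allocated. Several items in Tab. 1 plausibly depend on how the patient was before surgery: physical prehabilitation, active mobilisation on the first postoperative day, early oral feeding, and the pre-discharge check of pain control and mobility. EQ-5D-5L asks about mobility and pain. Patients who start better may therefore be both more adherent and better afterwards. A two-sample test of postoperative scores would credit that difference to adherence.

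The regression step does not secure the adjustment. Entry depends on univariate significance, and the baseline score is not among the listed candidates. Choosing confounders by their p-values is in any case a weak rule for a non-randomised exposure.

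The second problem is the form of the effect. A single reduction from 1.0 cannot describe both a scale on which higher is better and one on which higher is worse. The stakes are bias in a primary endpoint, lost precision, and a primary instrument whose planned direction of effect is unclear.

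**Working it through.** **1. The protocol's own figure.** Inputs from Sample size: p1 = 0.70, p2 = 0.64, difference 0.06, ratio r = 2 (below to above), alpha 0.04 taken as two-sided, and the stated beta of 0.8 read as power 0.80. Treat the two fractions as binomial proportions, with pooled p = (0.70 + 2 × 0.64)/3 = 0.66.

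- n(above) = [2.054 × √(1.5 × 0.66 × 0.34) + 0.842 × √(0.70 × 0.30 + 0.64 × 0.36/2)]² / 0.06² ≈ 776.1, rounded up to 777; total 2,331.
- With continuity correction: (776.1/4) × [1 + √(1 + 6/(776.1 × 2 × 0.06))]² ≈ 800.9, rounded up to 801; total 2,403, against 2,406 stated.
- The same settings for failure to RIOT (6.5% vs 13%) give 294 and a total of 882, against 885 stated.

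So the figure reproduces when a score fraction is handled as a yes/no rate. Read instead as a comparison of means, 802 and 1,604 patients imply an SD of 0.06 / [(2.054 + 0.842) × √(1/802 + 1/1604)] ≈ 0.479, essentially √(0.64 × 0.36) = 0.48. No SD of any PRO score is given.

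**2. What the named test would do with each possible PRO variable.**

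| Variable tested | Use of baseline |
|---|---|
| Postoperative score | None |
| Change from baseline | Subtracted with a fixed weight of 1 |
| Fraction of baseline | Divided out; fails at a baseline of 0 |

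None of these is an adjustment for baseline.

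**3. Bias.** Assumptions, none of them from the protocol: baseline-outcome correlation ρ = 0.5, equal variances before and after, and no adherence effect given baseline. The protocol's group sizes and its testing level of 0.05 are used. A baseline difference of d SD shifts the postoperative difference by ρd. The standard error is √(1/802 + 1/1604) = 0.0432 SD.

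- d = 0.05: shift 0.025, z = 0.58, rejection about 9%.
- d = 0.10: shift 0.050, z = 1.16, rejection about 21%.
- d = 0.20: shift 0.100, z = 2.31, rejection about 64%.

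The nominal rate is 5%. A change score does not remove the problem under these assumptions: its shift is ρd − d = −(1 − ρ)d, which at ρ = 0.5 is equally large in the opposite direction.

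**4. Precision.** With equal variances and baseline unrelated to group, the variance of the baseline-adjusted estimate is 1 − ρ² of that for the postoperative score alone and (1 + ρ)/2 of that for the change score.

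| Assumed ρ | vs postoperative score alone | vs change score |
|---|---|---|
| 0.3 | 91% | 65% |
| 0.5 | 75% | 75% |
| 0.7 | 51% | 85% |

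At ρ = 0.5 the gain equals 1/0.75 = 1.33, or about a third more patients.

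**5. Direction on MDASI-GI.** With 0 as no symptoms and 10 as the maximum, a fall to 0.70 or 0.64 of baseline means fewer symptoms after surgery, and the lower figure, assigned to low adherence, is the better result. That reverses the sizing assumption. On EQ-5D-5L items, where 5 is best, the same figures mean worsening. A patient with a baseline score of 0 has no ratio at all.

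**The case against.** The strongest reply is that the fraction appears only in the sample-size paragraph, where 1.0 may be a group-level normalisation, and that no text orders a division patient by patient. The t-test sentence is a general rule for all continuous variables, and the regression that follows could admit the baseline score. Scoring and exact covariates commonly belong in an SAP, which is not at hand. Much of this stands. What remains is that the protocol does state a method: unadjusted tests, then selection by univariate significance. That method does not secure the adjustment.

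Three stronger readings are tempting and are not supported:

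- *The baseline is wasted.* If the change or the fraction is what is tested, the baseline is used. The protocol leaves open which variable that is.
- *The fraction is undefined for MDASI-GI.* Strictly, it fails only for a patient whose baseline score is 0. The general fault is the reversed direction.
- *Delayed-urgency patients cannot have a baseline and drop out of the PRO analysis.* The term is undefined, no interval to surgery is given, and no rule excludes a patient whose baseline is missing or out of window.

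Two further points are fair. In non-randomised groups, baseline adjustment and change scores answer different questions, so the choice is not purely technical; that is a reason to fix it in advance. The precision ratios assume that baseline is unrelated to group, so they do not measure the confounding; the rejection rates in step 3 of the working illustrate that separately.

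**Conclusion.** The concern holds in a limited form. The stated analysis does not ensure that the preoperative score enters the comparison of non-randomised adherence groups, although the score is collected. Confounding by baseline is therefore possible, but the documents do not show that it will occur. Its size depends on an unknown imbalance: at ρ = 0.5, differences of 0.05 to 0.2 SD would raise the false-positive rate from 5% to between about 9% and 64%. The precision at stake, with baseline unrelated to group, is a variance of about 75% of the unadjusted value at ρ = 0.5, ranging from 91% to 51% over ρ of 0.3 to 0.7. All correlations are assumptions.

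The mismatch between a reduction from 1.0 and MDASI-GI needs no assumption beyond applying the sizing statement, which names no instrument, to that primary questionnaire.

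The baseline window for all enrolled patients may not be achievable in delayed urgency. This is an unreconciled pair of statements, not a demonstrated loss of patients. The change is worth making, but the study does not fail without it.

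**What to change.** - For each PRO instrument, on its own scale and with its direction stated, prespecify a linear or mixed model of the postoperative score on adherence, the baseline score of the same instrument, prespecified confounders and centre. The baseline score is always included and is not subject to univariate screening.
- State which postoperative time point is primary.
- Report the adjusted mean difference with its 95% confidence interval. Do not use the fraction of baseline as the analysed outcome.
- Add a rule for missing baseline scores, because a complete-case model would lose those patients.
- Reconcile the four-to-one-week window with the admission of delayed-urgency patients: define the category and say which baseline questionnaire counts for it. The forms already carry a completion date and a preoperative tick box, so no new data item is needed.

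The cost is a few lines of text, slightly more analysis work and the missing-baseline rule. No extra visit or questionnaire is required.
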